The Effect of Platelet Rich Plasma on Non-scarring Alopecia

PI: [name]

NCT03689452

Document Date: 9/21-2018

The Effect of Platelet Rich Plasma on Non-scarring Alopecia: A Randomized, Controlled Clinical Trial

Identifiers: GCO: 18-1714 IF2274490

IRB: IRB-18-00297

Investigators: [name] [name] [name] [name]

Study Site:
Mount Sinai School of Medicine
Department of Dermatology

New York, NY 10028

Financial Support:

Eclipse

Protocol Version: 2

Date: 9/21/18

The Effect of Platelet Rich Plasma on Non-scarring Alopecia: A Randomized, Controlled Clinical Trial

Introduction and rationale:

The purpose of this study is to evaluate the clinical efficacy of platelet rich plasma (PRP) injections for non-scarring alopecia in women. A randomized, placebo-controlled clinical trial will be performed where patients with non-scarring alopecia will either receive injections of their own PRP or injections of normal saline (placebo). Patients in the treatment group (Group A) will have a small amount of their own blood drawn (22 mL) and have their PRP injected into their scalp. The injections will be given at weeks zero, four, eight, and twenty-four. The number of injections in the PRP group will vary slightly based on how much PRP is able to be extracted from the patients' blood. However, typical number of injections will range from 10-30 with 0.2 mL injected into each site. The placebo group (Group B) will be given the same schedule but will receive sham injections only composed of normal saline (3 mL, total of 15 injections with 0.2 mL in each injection site). In place of the blood draw, the placebo group will have a sterile needle placed into the ante-cubital fossa but no blood will be taken from the patient. Both groups will have clinical data collected at all visits, including a screening visit before enrollment and a final assessment visit at week 40, for a total of six study visits per patient. Data collection will include representative photographs of the scalp and measurements of hair thickness using a specialized camera called a folliscope as well as a standard digital camera for macroscopic photos. No hair samples will be needed for photographs and there will be no biopsies taken during this study. The results from the two groups will then be compared. Patients will also be given small surveys at the beginning, middle and end of the study to assess for any pain, adverse effects, and the level of improvement the subjects have seen.

In summary, all study participants will have a screening visit before enrollment, 4 study visits for subdermal scalp injections, and one final assessment visit at week 40. Data analysis and comparison will be measured with macroscopic photography and microscopic hair follicle photography as well as with patient surveys.

Objective:

To evaluate the clinical efficacy of platelet rich plasma (PRP) injections for non-scarring alopecia in women .

Description of Study:

Subjects receiving PRP injection will undergo the following protocol:

All subjects will be asked to wear dark, non-visible goggles during the blood draw in the beginning of the visit. 22 mL of whole blood will be drawn from a peripheral vein and then processed through a centrifuge two times thus obtaining about 3-6 mL of plasma rich in leukocytes and platelets. The doctor will leave the room for approximately 10 -15 minutes to prepare the PRP injections. The subject's scalp will be cleansed topically with alcohol and then injected with the patient's PRP using a 25-gauge needle in a 3 mL Luer-lock syringe into the subcutaneous scalp. Injections will be 1-2 cm part and the amount injected will be 0.2 mL per injection. The number of injections in the treatment group will vary from patient to patient depending on the amount of PRP that was able to be harvested from the blood draw. However,

patients can expect anywhere from 10-30 injections. There will not be more than 30 injections in any patient during any study visit.

Subjects receiving placebo (preservative-free normal saline) will undergo the following protocol: All subjects will be asked to wear dark, non-visible goggles during the blood draw period in the beginning of the visit. The patient in the control group will have a sterile needle placed by a certified doctor or medical assistant into the ante-cubital fossa of the arm but no physical blood will be taken out of the patient. The doctor will leave the room for approximately 10 -15 minutes to prepare the normal saline injections. The subject's scalp will be cleansed topically with alcohol and then injected with 0.9% normal saline, for a total of 3 mL, (0.2 mL in each injection site and 15 total injections). The injection sites will be 1-2 cm apart.

Protocol Schedule:

- 1. Study visit 1: screening visit with the clinical research team after referral from Hair loss clinic with prior baseline blood work already reviewed
- 2. Study visit 2: Injection #1, week 0: FULL PHOTO EVALUATION AND SURVEY #1
- 3. Study visit 3: Injection #2, week 4
- 4. Study visit 4: Injection #3, week 8: FULL PHOTO EVALUATION
- 5. Study visit 5: Injection #4, week 24: FULL PHOTO EVALUATION AND SURVEY #2
- 6. Study visit 6: final assessment visit only, no injections, week 40: FULL PHOTO EVALUATION AND SURVEY #3

At each injection visit (weeks 0,4,8,24) the participant will first speak to the doctor and discuss any adverse reactions. Photographs will be taken as mentioned above. On certain visits, as listed, patient surveys will be given to subjects to assess PRP, any improvements in the alopecia, pain or other adverse effects. The data from these surveys will be used in the final stages of the research to look at patient aggregated data. After this, the injection protocol will be followed as detailed above and the patient will be scheduled for their next appointment.

Patients will be contacted within 12-24 months post study to be informed of results of the study. If possible and if published by this time, a copy of the paper outlining the trial will also be provided to patients.

Primary endpoint:

Photographs of the scalp (with standard digital camera) and trichoscopy photographs (with specialized camera called folliscope to visualize hair follicles and measure hair thickness, density, and caliber where the follicle exits the scalp) will be used for primary evaluation endpoint.

Secondary endpoint:

Additionally, surveys as detailed above will provide qualitative participant information regarding improvement with procedure, pain or other adverse effects.

Subject Selection:

Inclusion Criteria

- 1. Must understand and voluntarily sign an informed consent form
- 2. Must be female between the ages of 18 and 65 years at the time of consent
- 3. Must be able to adhere to the study visit schedule and other protocol requirements
- 4. Documented baseline blood work either in chart review or documented by the hair loss clinician- blood work needed includes normal TSH and ferritin as per the laboratory standards, platelet count above 150,000 platelets per microliter and a negative pregnancy test for any premenopausal women—all blood work must be documented as normal within 12 months prior to the start of the study

Exclusion Criteria

Because of the parameters of the study, a chart review and subject interview will be conducted during the screening visit. "Yes" answers to any of the following will result in inability to participate in the study.

- Previous or current use in the last 1 year of finasteride, minoxidil topical or oral, or spironolactone
- A diagnosis of non-androgenic alopecia (i.e.: another diagnosis for the alopecia)
- Abnormal Baseline ferritin, TSH, platelet count, and a negative urine pregnancy test in any pre-menopausal female in past 12 months.
- Active skin disease (Psoriasis or severe seborrheic dermatitis) of the scalp
- Active scalp infection
- Severe active blood infection
- Cuts or abrasions on the scalp
- History of surgical hair restoration
- Current or recent malignancy
- History of systemic chemotherapy or radiation
- History of thyroid dysfunction
- History of autoimmune disorder (specifically Graves disease, hashimoto thyroiditis, or systemic lupus erythematosus)
- Tendency to develop keloids
- Continued medically necessary daily use of Nonsteroidal anti-inflammatory or Vitamin E
- Platelet dysfunction syndrome
- Thrombocytopenia less than 150,000
- Diagnosis of hypofibrinogenemia
- Anticipated pregnancy or trying to become pregnant in the next 2 years
- Current or active Tobacco use

Informed Consent:

Prior to entering the study, the investigator or designated assistant will explain to each subject the nature of the study, its purpose, procedures, expected duration, alternative therapy available, and the benefits and risks involved in study participation. Subjects will be given the consent document, the opportunity to ask questions, and will be informed of their right to withdraw from the study at any time without prejudice. After this explanation and before any study-specific procedures have been performed, the subject will voluntarily sign and date and informed consent form, including photographic consent form. Prior to participation in the study, the subject will receive a copy of the signed and dated written informed consent form.

Platelet Rich Plasma (PRP) And Saline Injection Guidelines:

3-6ml of PRP will be injected into randomly assigned subjects. The same procedure will be carried out for administration of the normal saline. Both procedures are detailed above.

Safety Evaluations:

Adverse Reactions

At each visit, the subjects will be assessed for any of the following possible AEs:

- -injection site pain
- -ecchymoses
- -systemic effects, including nausea, fatigue, malaise, flu-like symptoms, headache, runny nose, diplopia, dysarthria, generalized muscle weakness, asthenia, blurry vision, ptosis, dysphagia, dystonia, urinary incontinence, breathing difficulties, rash.

Prior And Concomitant Medications:

At the initial visit, prior and concomitant medications and therapies will be reviewed as may pertain to exclusion from the study.

Restricted Medications/Treatments:

The restricted medications and treatments prior to the study initiation are those that the investigator feels may indicate that the patient has an unstable medical condition, as described in the exclusionary criteria.

Subject Withdrawal Or Discontinuation:

Subjects may choose to withdraw from the study or may be withdrawn by the investigator at any time without prejudice to their future medical care. Any subject who does not comply with the inclusion/exclusion criteria may be withdrawn from further participation in the study.

Discontinuation Procedures:

Any subject who wishes to discontinue prematurely from the study should return to the study center for an End of Study Visit.

Adverse Event Definitions:

An adverse event (AE) is any untoward medical occurrence in a patient or clinical investigation subject which is temporally related to protocol procedures, including administration of a

pharmaceutical product at any dose, but which does not necessarily have a causal relationship with the treatment. The term AE also applies to laboratory findings or results of other diagnostic procedures that are considered to be clinically relevant (e.g., that required unscheduled diagnostic procedures or treatment measures or result in withdrawal from the study). Surgical procedures themselves are not adverse events; they are therapeutic measures for conditions that require surgery. The condition for which the surgery is required is an adverse event, if it occurs or is detected during the study period. Planned surgical measures permitted by the clinical study protocol and the condition(s) leading to these measures are not adverse events, if the condition(s) was (were) known before the start of study treatment.

Adverse events will be recorded according to CTCAE guidelines.

A serious adverse event (SAE) is any AE or adverse drug reaction that at any dose results in any of the following outcomes:

- death
- life-threatening adverse event
- inpatient hospitalization or prolongation of existing hospitalization
- persistent or significant disability/incapacity
- congenital anomaly/birth defect

An event may be considered serious when, based upon appropriate medical judgment; it jeopardizes the patient or subject and may require medical or surgical intervention to prevent one of the outcomes listed above.

A life-threatening adverse event is any AE or adverse drug reaction that at any dose places the patient or subject, in the view of the investigator, at immediate risk of death from the reaction as it occurred. It does not include a reaction or event that, had it occurred in a more severe form, might have caused death.

Materials And Supplies:

Study Device

Eclipse will manufacture and provide the PRP collection kits for use in the study. The PRP will then be injected into the scalps of patients for the treatment arm of the study. Normal saline will be used for the placebo arm of the study.

Syringes and 25 G needles will be used.

Gauze, alcohol swabs will be used to prepare the injection sites.

Institutional Review Board:

Prior to beginning this study, approval must be obtained from the Institutional Review Board at the Mount Sinai Medical Center.

Data Analysis:

Individual efficacy variables, the sum of those variables, and safety parameters will be analyzed.

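### Subjective adverse events at weeks 4, 8 and 24 are first elicited by the doctor, a role that can know the arm; a self-report form completed beforehand is a cheap improvement.

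*Protocol*

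**What the plan says.** The paragraph after the visit list in the Protocol Schedule covers the injection visits at weeks 0, 4, 8 and 24. At these, "the participant will first speak to the doctor and discuss any adverse reactions". Photographs, any scheduled survey and then the injections follow.

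The Description of Study gives product preparation to the same role in both arms: "The doctor will leave the room for approximately 10 -15 minutes to prepare the PRP injections" for PRP, and "The doctor will leave the room for approximately 10 -15 minutes to prepare the normal saline injections" for placebo. The two preparations do not look alike. For PRP, "22 mL of whole blood will be drawn from a peripheral vein and then processed through a centrifuge two times". For placebo, a needle is placed "into the ante-cubital fossa of the arm but no physical blood will be taken out of the patient". The only masking measure described applies to the participant: "All subjects will be asked to wear dark, non-visible goggles during the blood draw".

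Under Safety Evaluations, participants are assessed at every visit against a fixed list, most of it symptoms; no assessor is named. Adverse Event Definitions calls for recording by CTCAE and names no grader. The secondary endpoint rests on participant surveys, which also cover pain and adverse effects; these are scheduled at weeks 0, 24 and 40. On analysis, the Protocol says: "Individual efficacy variables, the sum of those variables, and safety parameters will be analyzed". The SAP contains no adverse event analysis.

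**The concern.** Pain, fatigue, malaise, headache and nausea are recorded only if the participant mentions them or is asked. How readily they surface depends on how the question is put and how far it is pursued. If the questioner knows who received PRP, the arms can differ in recorded events with no difference in true events, and a true difference can be hidden in the same way. The direction cannot be predicted.

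What is at stake is mainly the safety analysis promised under Data Analysis. The sham venepuncture and the goggles show an intention to keep participants masked. A masked participant's report is useful for comparing the arms if it is captured before someone who knows the allocation shapes it. This point concerns only the collection of safety data, not the reading of the density and caliber images.

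**Working it through.** There is no figure in the documents to reproduce: neither the protocol nor the SAP gives a sample size, an event rate or an adverse event test. The check is therefore a reading of the text, followed by an illustration on stated assumptions.

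**Exposure by visit**

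| Week | Doctor conversation specified | Survey | Can the doctor know the arm when asking? |
|---|---|---|---|
| 0 | Yes | #1 | Not from preparation: the conversation precedes the first preparation |
| 4 | Yes | None | Yes |
| 8 | Yes | None | Yes |
| 24 | Yes, placed first | #2 | Yes |
| 40 | Not specified; assessor unnamed | #3 | Not stated |

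The exposed visits are weeks 4, 8 and 24. At weeks 4 and 8 no self-report is scheduled. Survey #2 comes 24 − 8 = 16 weeks after the third injection and, on the described order, after the conversation.

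**Exposure by type of event**

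Non-serious symptoms are the vulnerable group. Ecchymoses, rash and ptosis can be seen, and the serious adverse event criteria are tied to outcomes such as death and hospitalization. Both are less dependent on questioning.

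**Illustration (all inputs assumed)**

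Let the true proportion with a reportable event be 0.50 in both arms. Observed proportion = true proportion × probability that it is recorded.

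- Saline: 0.50 × 0.60 = 0.30
- PRP, milder gap: 0.50 × 0.70 = 0.35; risk ratio 0.35 / 0.30 = 1.17
- PRP, larger gap: 0.50 × 0.80 = 0.40; risk ratio 0.40 / 0.30 = 1.33

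With n per arm and x₁, x₂ participants with a recorded event, the Pearson statistic is X² = 2n(x₁ − x₂)² / [(x₁ + x₂)(2n − x₁ − x₂)]. The test rejects at two-sided 5% when X² > 3.84. The rejection probability is the sum of Bin(x₁; n, p₁) × Bin(x₂; n, p₂) over all pairs that reject.

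| Recorded, saline v PRP | 30 per arm | 60 per arm |
|---|---|---|
| 30% v 30% (no bias) | 4.9% | 5.2% |
| 30% v 35% | 6.7% | 9.2% |
| 30% v 40% | 12.3% | 21.0% |

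The milder gap barely moves the false positive rate at 30 per arm; the larger one multiplies it by about 2.5 (12.3 / 4.9) at 30 per arm and 4 (21.0 / 5.2) at 60.

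**The case against.** The strongest reply is that participants already report for themselves. The secondary endpoint is survey-based, and at week 40 the survey is not stated to follow a doctor conversation. That stands, and it limits the point: the secondary endpoint is only partly exposed. It does not cover weeks 4 and 8, or the order at week 24.

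Second, a fixed event list and CTCAE recording limit improvisation. In part they do. A list fixes the topics, but not how far each is pursued or what counts as enough to record.

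Third, different people may prepare the product and ask the questions. The protocol lists several investigators, so this is possible, but nothing requires it. The point is about a role, not one individual.

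Fourth, the stated objective is efficacy, and the SAP tests only density and caliber. That is right, and it is why this is a modest improvement and not a threat to the main result.

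A reader might go further and infer that the doctor also grades events with knowledge of the arm. The documents name no grader, so that remains an inference. A reader might also infer that the placebo control becomes worthless for safety. The documents do not support this either: serious events and observable signs are less exposed, and the surveys allow some cross-check.

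**Conclusion.** The point holds as a cheap improvement, limited to non-serious subjective adverse events at weeks 4, 8 and 24. It rests on three features of the text: one role both prepares the product and takes the first adverse event history, no masking of staff is described, and safety parameters are to be analyzed. The text establishes that arm-aware elicitation is possible, not that it will occur.

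Its size is unknown. The illustrative rejection rates run from 6.7% to 21.0%, against about 5% without bias, and depend wholly on the assumed event rate, recording probabilities and sample sizes. The primary efficacy comparison is unaffected.

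**What to change.** Change the Protocol Schedule sentence so that at weeks 4, 8, 24 and 40, and at week 0 as a pre-injection baseline, the participant completes a short self-report symptom form before she speaks to the doctor. Build it from the existing Safety Evaluations list, put into lay wording, and attach it to the survey where one is already scheduled.

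Use the presence or absence of each self-reported symptom as the source for comparing subjective events between arms. The doctor may still clarify, add and grade events for safety oversight, but may not delete a self-report. Report doctor-added events and CTCAE grades separately, labelled as unblinded. The form deals with elicitation only; any bias in grading remains, hence the label.

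The cost is a wording change, a short form at each of five visits, and the work of turning clinical terms such as dysarthria and asthenia into plain language. No extra staff or procedures are needed. More trivial events will be captured, but by the same process in both arms.

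### At week 24 the self-rated improvement survey follows a talk with a doctor who may know the arm, and no order is set for week 40; completing it on arrival removes that same-visit cue

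*Protocol*

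**What the plan says.** In the protocol, the paragraph after the visit list under Protocol Schedule sets out the injection visits at weeks 0, 4, 8 and 24. It opens with "the participant will first speak to the doctor and discuss any adverse reactions". Next comes "Photographs will be taken as mentioned above". On the visits so listed, "patient surveys will be given to subjects to assess PRP, any improvements in the alopecia, pain or other adverse effects". The sequence closes with "After this, the injection protocol will be followed as detailed above".

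The visit list places Survey #1 at week 0, Survey #2 at week 24 and Survey #3 at week 40. Week 40 is an assessment visit without injections, so the paragraph does not cover it.

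Under Description of Study, the PRP arm has "The doctor will leave the room for approximately 10 -15 minutes to prepare the PRP injections" and the saline arm has "The doctor will leave the room for approximately 10 -15 minutes to prepare the normal saline injections". The only masking measure described is goggles for the participant around the blood draw.

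The Secondary endpoint section names the surveys as the source of qualitative information on improvement, pain and adverse effects. The summary at the end of the Introduction gives them a place in the comparison: "Data analysis and comparison will be measured with macroscopic photography and microscopic hair follicle photography as well as with patient surveys". The SAP specifies tests for hair density and caliber and none for the surveys.

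**The concern.** A participant's own rating of improvement is only as good as her ignorance of her arm. If she has just spoken with someone who knows it, the manner of that talk could colour the form she fills in next, differently in the two arms and without anyone intending it. The topics overlap: the conversation is about adverse reactions, and the survey asks about adverse effects and pain as well as improvement.

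At stake is the patient-reported part of the trial. A difference in ratings produced this way would look like a benefit of PRP, or could hide one, and analysing the survey answers alone could not tell a cue from an effect. The hair measurements give some check, because full photo evaluations are also scheduled at weeks 24 and 40. A mismatch between ratings and measurements would be visible, but it would not show that cueing was the cause.

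**Working it through.** The plan gives no figure on this point, so the check sets the passages side by side.

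**1. Is an order really written?** Yes, for injection visits. The paragraph says the talk comes first, and it places the injections after the steps already described. Photographs and surveys lie between. So the survey follows the talk and precedes that day's injections.

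**2. Which surveys does it govern?**

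| Survey | Week | Injection visit? | Written order applies? | Can it rate treatment benefit? |
|---|---|---|---|---|
| #1 | 0 | Yes | Yes | No, it precedes the first injection |
| #2 | 24 | Yes | Yes | Yes |
| #3 | 40 | No | No order given | Yes |

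The order governs 2 of 3 surveys, but only 1 of the 2 post-baseline ones. Week 24 is a stated order; week 40 is a silence.

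**3. Can the doctor know the arm?** The same role title is used for the conversation and for preparing the injections in both arms. PRP preparation starts from a 22 mL blood draw spun twice, whereas the saline arm has no blood taken. Whoever prepares the syringe can therefore tell which it is. The documents neither mask this role nor assign the conversation to someone else. By week 24 three injection sessions (weeks 0, 4 and 8) have already taken place.

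**4. What would moving the survey remove?** Conversations up to and including week 24 fall at weeks 0, 4, 8 and 24, which makes 4. Completing Survey #2 on arrival takes the week 24 conversation out of its path: 4 − 1 = 3 remain. By week 40 all 4 injection-visit conversations have happened, and arrival completion can prevent only a further one at that visit. The injection count is a separate possible cue that stays: 10 to 30 with PRP against a fixed 15 with saline.

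**5. Would anything be lost?** No survey content. The form already precedes that day's injections, so its pain and adverse-effect items would refer to the same earlier injections as they do now.

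**6. A related inconsistency.** The Description of Study puts the blood draw (or sham needle) at the beginning of the visit, whereas the Protocol Schedule puts the conversation first and the injection procedure later. The two need to be reconciled. Completion on arrival would precede both.

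**The case against.** The strongest reply is that survey order is a minor consequence of a larger gap, the unstated masking of the doctor. Three earlier conversations and three injection sessions precede Survey #2 whatever is done at week 24, so a participant who picks up cues has had ample chance already. Masking the doctor or separating the staff roles would deal with the source. This stands, and it limits what the change can achieve. It does not make the change pointless, because the contact closest to the rating is also the easiest to remove.

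Second, the mechanism is inferred. The documents do not say that the doctor who talks is the doctor who prepares, several investigators are listed, and the stated subject of the talk is adverse reactions rather than progress. This also stands: the text supports *may know the arm* and no more. A reader might infer that the doctor is known to be unmasked and that ratings will be contaminated. The documents establish neither.

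Third, the surveys are called qualitative and the SAP plans no test of them. That limits the consequence but does not remove it. The protocol still lists the surveys among its comparison measures, and a descriptive comparison can be distorted in the same way as a tested one.

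**Conclusion.** The point holds as a cheap improvement to the visit order. At week 24 the text places the first post-treatment rating of improvement after a conversation with a doctor who may know the arm. At week 40 no order is given. It rests on reading the paragraph as a sequence, which its wording supports, and on the inference that someone who prepares the injections can know the assignment.

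Three stronger readings are not supported:

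- **That the whole secondary endpoint is affected by the written order.** The order reaches one of two post-baseline surveys.
- **That moving the survey would solve the problem.** It removes the same-visit cue only; earlier contacts and the injection counts remain.
- **That an inflated false-positive rate can be attached to it.** The SAP contains no survey test, and the documents give no sample size, survey scale or standard deviation. Any such rate would describe an analysis that is not planned, with an assumed shift.

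The point does not bear on the SAP's tests of hair density and caliber. Whether those images are read blind is a separate question.

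**What to change.** Add to the paragraph after the visit list: *At weeks 0, 24 and 40 the survey is handed out on arrival, and is completed and collected before the participant speaks to the doctor and before photographs are taken.* The adverse-reaction discussion, photographs and injections then follow as written. Weeks 24 and 40 are the ones that matter; week 0 is included for consistency.

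Preferably the form is handled by someone who neither prepares the injections nor places the needle, since the saline procedure allows a medical assistant to do the latter.

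The text should not bar the doctor from seeing the completed form before the injections. The form also records pain and adverse effects, and collecting it before the conversation is enough for the purpose here.

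Reconcile the Description of Study with the Protocol Schedule on whether the draw or the conversation opens the visit.

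The cost is a wording change, a few minutes at arrival, and someone to hand out and collect the form. No visit or study procedure is added.

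### The pregnancy test may be 12 months old at entry and none is scheduled in the trial, so an unrecognised pregnancy at week 0 is not screened out

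*Protocol*

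**What the plan says.** The trial enrols women aged 18 to 65, so many may be premenopausal. Four parts of the protocol bear on pregnancy at entry.

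- **Inclusion Criteria, item 4.** The required results include "a negative pregnancy test for any premenopausal women", alongside TSH, ferritin and platelets. They may come from existing records: "Documented baseline blood work either in chart review or documented by the hair loss clinician". One time limit covers them all: "all blood work must be documented as normal within 12 months prior to the start of the study".
- **Protocol Schedule, item 1.** Study visit 1 is a "screening visit with the clinical research team after referral from Hair loss clinic with prior baseline blood work already reviewed". No laboratory or urine test is listed for it.
- **Protocol Schedule, later visits.** The visits at weeks 0, 4, 8, 24 and 40 list photographs, surveys and injections in various combinations. The text after the schedule adds "At each injection visit (weeks 0,4,8,24) the participant will first speak to the doctor and discuss any adverse reactions". No pregnancy test appears.
- **Exclusion Criteria.** These are checked as follows: "a chart review and subject interview will be conducted during the screening visit". One bullet reads "Abnormal Baseline ferritin, TSH, platelet count, and a negative urine pregnancy test in any pre-menopausal female in past 12 months". Another reads "Anticipated pregnancy or trying to become pregnant in the next 2 years". None names current pregnancy or recent delivery.

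The SAP does not address eligibility.

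**The concern.** The protocol plainly means to keep pregnant women out: it asks for a negative test and excludes women who expect or are trying to conceive. A pregnancy test speaks only to the time at which it was taken. Putting it under the same look-back as ferritin and TSH lets a result stand in for the subject's status at week 0 when it may be older than a full pregnancy, and nothing later in the schedule corrects this.

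What is at stake is mainly whether the entry rule does its own job. A woman whom the sponsor intended to exclude could be randomised and injected without any stated check having failed. The time limit is also counted back from the study's start, which is not defined as the subject's own week 0.

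**Working it through.** The plan gives no calculated figure to reproduce. The check is a reading of every criterion and visit, plus one subtraction.

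**Inputs**

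- Permitted age of the result: 12 months, about 52 weeks (inclusion item 4; the 12 months are repeated in the exclusion bullet).
- Pregnancy tests scheduled from screening to week 40: none.
- Length of a pregnancy: 38 to 40 weeks. This is an assumption; the documents do not give it.

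**Does the 12-month limit really govern the pregnancy test?** Item 4 states its limit for blood work, while the exclusion bullet speaks of a urine test, so one might argue that the limit does not reach it. But item 4 lists the pregnancy test as part of the blood work needed, and the exclusion bullet attaches 12 months to the urine test directly. Both routes give the same window.

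**Arithmetic.** Slack = permitted age − length of pregnancy.

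- With 40 weeks: 52 − 40 = 12 weeks.
- With 38 weeks: 52 − 38 = 14 weeks.

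A negative result at week −52 can therefore precede conception and a complete pregnancy, with 12 to 14 weeks left before week 0. It also precedes any conception in the 38 to 40 weeks before week 0, which is when a pregnancy still in progress at week 0 would have begun. At the old end of the window the result carries no information about pregnancy at week 0.

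**Who is stopped by the remaining criteria, read as evidently intended?**

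1. *Knows she is pregnant.* Probably stopped. She would reasonably answer yes to the interview question on pregnancy in the next 2 years, although the wording looks forward and does not name current pregnancy.
2. *Has a positive test on record.* Stopped by item 4 and the chart review. No new test is required, however, so a positive result need not exist.
3. *Pregnant, unaware of it, not planning a pregnancy, negative test on file within 12 months.* Not stopped. Item 4 is met, she truthfully answers no to the interview question, and no other criterion or visit would reveal the pregnancy.
4. *Recently delivered.* Stopped if her hair loss has been given a diagnosis other than androgenic alopecia, since that is an exclusion. If not, and no further pregnancy is planned, no criterion mentions the delivery.

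Case 3 is the gap.

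**A contradiction alongside it.** Item 4 requires a negative test. The exclusion bullet, read word for word, lists a negative test as a reason for exclusion. Taken literally, no premenopausal woman with a negative test could satisfy both.

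**The case against.** The strongest reply is that the criteria work together. Subjects come by referral from a hair loss clinic, charts are reviewed, and each woman is interviewed about pregnancy plans before enrolment. Hair loss with another diagnosis is excluded. This stands as far as it goes: it disposes of cases 1 and 2 and part of case 4. It does not reach case 3, because neither an interview nor a record review detects a pregnancy that the woman does not know about. Detecting that pregnancy is the purpose of a test.

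Several stronger readings are tempting, and the documents do not support them.

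- *That any pregnant or recently delivered woman passes every stated criterion.* She does not. The interview and the other-diagnosis exclusion catch some, and the literal wording of the exclusion bullet means that no premenopausal woman with a negative test passes every criterion.
- *That results could be much older than 12 months, because the limit is counted from the trial's start date.* The phrase is open to that reading, but no recruitment period is given, and the exclusion bullet, asked at the subject's own screening visit, points to a subject-level window. The ambiguity calls for a clarification and supports no figure.
- *That the age of the test at weeks 8, 24 or 40 adds to the problem.* Those ages do not bear on eligibility at week 0.
- *That pregnancy or delivery would put large changes into the SAP's difference scores.* The documents say nothing about such an effect or how many subjects it might touch. With randomised allocation, such cases would mainly add noise, not systematic bias.
- *That 12 months is also too long for TSH, ferritin and platelets.* No figure in the documents shows this. Thyroid dysfunction and low platelets have their own exclusions.

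The documents also describe no specific hazard of the injections in pregnancy. The point rests on the protocol's evident intention to exclude pregnant women.

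**Conclusion.** The point holds in a limited form. A negative pregnancy result up to about 52 weeks old satisfies entry, no test is scheduled at screening or afterwards, and current pregnancy is not named anywhere in the criteria. Under an assumed pregnancy of 38 to 40 weeks, the window exceeds a whole pregnancy by 12 to 14 weeks, so the rule as written cannot do what it plainly intends. The woman it misses is premenopausal, with an unrecognised and unplanned pregnancy at week 0.

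How often this would happen cannot be estimated from the documents, and no effect on the efficacy comparison is claimed. The conclusion depends on two things: the assumed length of pregnancy, and reading the exclusion bullet as intended (a positive test excludes) instead of literally. It should be corrected because it concerns who may be injected and the repair is cheap.

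**What to change.** - Take the pregnancy test out of the 12-month laboratory window in inclusion item 4 and in the exclusion bullet, and tie it to the subject's own enrolment. Use the urine test the protocol already names, at an existing visit before randomisation. The documents do not say at which visit allocation takes place or how long screening may precede week 0, so the amendment should state where the test falls relative to both.
- Name current pregnancy in the existing screening interview.
- For TSH, ferritin and platelets, count the window back from the subject's week-0 visit in place of the study's start.
- Reconcile item 4, which requires a negative test, with the exclusion bullet, which lists one as a reason for exclusion.
- Whether and how recent delivery is handled is for the sponsor to decide. The documents give no basis for a particular rule.

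The cost is one urine test per premenopausal subject at a visit already planned, one interview question and a wording amendment. The downside is a few more screen failures.
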